## **14.6 Reporting Urgent Safety Measures**

The Sponsor and Investigators may take appropriate urgent safety measures in order to protect the participants against any immediate hazard to their health or safety. The CI must telephone the NPRA to discuss the circumstances leading to the decision and the proposed measures to be taken. No later than 3 days following the conversation the CI must give written notice to the NPRA of that conversation and agreed actions. The Sponsor must also receive a copy of this communication to facilitate oversight of participating PI and participating site notification of imposed safety measures. A formal Substantial Amendment will be required for preparation and submission to the relevant

ethics committee/NMRR and NPRA at the earliest opportunity. Refer to sponsor SOP Management of Amendments for guidance.

## 14.7 Notification of Serious Breaches of GCP and/or the protocol

Any Study Deviations or Violations will be documented using Sponsor's Protocol Deviation form, and entered onto the Sponsor's log. Potential Serious Breaches and Urgent Safety Measures will be reported according to SOP.

A "serious breach" is a breach which is likely to effect to a significant degree :

- (a) The safety or physical or mental integrity of the participants of the trial; or
- (b) The scientific value of the trial

The CI or the CI delegate will notify the Sponsor immediately of any case where there exists a possible occurrence of a serious breach.

# 15. Data management and quality assurance

#### **15.1 Confidentiality**

All data will be handled in accordance with the Data Protection Act. The Case Report Forms (CRFs) will not bear the participant's name or other directly identifiable data. The participant's trial Identification Number (ID) only will be used for identification. The Sponsor Subject ID log can be used to cross reference participant's identifiable information.

#### 15.2 Data collection tool

Case Report Forms will be designed by the CI and the CI delegate and the final version will be approved by the Sponsor.

It is the Investigator's responsibility to ensure the accuracy of all data entered and recorded in the CRFs. The Staff Delegation of Responsibilities Log will identify all trial personnel responsible for data collection, entry, handling and managing the database. Basic demographic and clinical information will be gathered at the time of the initial interview and by review of the medical notes if needed. The following information will be recorded for all subjects in the CRF:

- Demographic details: Date of enrolment, age, gender, ethnicity
- Clinical data: symptomatology, risk factors for development of CRC, weight, height, vital signs
- Findings at endoscopy
- Imaging: findings of ultrasound, CT and/or MRI (performed as clinically indicated)
- Disease staging: TNM staging prior to surgery and definitive histological staging (TNM, Duke's stage)
- Histology: routine histological grading, apoptosis count and specialist assays (see below)
- Concomitant medication: a full record of all non-study drugs taken will be kept
- Study-drug treatment: compliance with study medication, all adverse events, serious or otherwise
- Validated Quality of Life Tool (EORTC QLQ C-30, EuroQol EQ-5D, QLQ-CR29)

The following blood sample analysis will be performed:

- Baseline FBC, urea and electrolytes, LFTs, CEA, pre-treatment serum sample for study molecular analyses
- Day 14/15 of treatment FBC, urea and electrolytes, LFTs, CEA, post-treatment serum sample for study molecular analyses
- Day 28 FBC
- Day 42 (4 weeks post-surgery) FBC, urea and electrolytes, LFT, CEA
- 6 monthly visits for 5 years following surgery CEA
- Serum plasma samples will be taken at baseline (Day 1) and end of treatment (Day 14), processed and stored at -80°C (+/- 10°C) for future analyses
- Any other blood or clinical sample at any time if deemed necessary by the investigators in case of a suspected adverse event

All laboratory analysis should be reviewed by the PI and where results reported are not within the normal range the PI must clearly annotate 'Not clinically Significant' or 'Clinically Significant' and sign and date the results. The relevant results should be carefully transcribed to the Case Report Forms.

In order to ensure completeness of data collected, participants will be contacted by the research team (telephone call/email) in the event of missing data such as patient quality of life questionnaires.

## 15.3 Incidental findings

Incidental findings arising during the study will be discussed with the medical and research team involved in the patients care. The medical and research team will always act in the patient's best interest and take appropriate clinical action in accordance with good clinical practice.

#### 15.4 Data handling and analysis

Data will be stored in anonymised form in a password-protected database. We will use a 44 Randomize44 study database storage programme. Study documentation will be stored for fifteen years after the completion of the study. Quality Control will be applied at each stage of data handling to ensure that all data are reliable and are processed correctly. Study data is destroyed after period of storage.

# 16. Archiving arrangements

The trial essential documents (e.g. TMF) along with the trial database will be archived in accordance with the sponsor SOP. The agreed archiving period for this trial will be defined within the Delegation of Duties Sponsorship Agreement.

# 17. Statistical design

#### 17.1 Statistical input in trial design

[name] [name] – Senior Lecturer in Biostatistics, provided statistical expertise in clinical trial design and statistical planning. [name] will conduct the statistical analyses and data interpretation as data is now being combined from 2 studies implementing the same protocol

(NeoART-UK and NeoART-Vietnam). [name] is also providing the statistical expertise and support for NeoART-Vietnam.

#### 17.2 Endpoints

## 17.2.1 Primary endpoints

The primary endpoint for the main comparison between the artesunate treatment and placebo arms will be persistent disease or disease recurrence, two years following surgery. All analyses will be made on an intention to treat basis, although per protocol analyses will also be reported. Statistical significance will be assumed at the 5% level unless otherwise indicated.

#### 17.2.2 Secondary endpoints

Secondary endpoints will include:

- Overall survival at 2 and 5 years
- Recurrence free survival at 5 years
- Colon cancer specific death at 2 and 5 years
- Artesunate drug related toxicity
- Adverse events
- Pathological assessment of tumour regression (involvement of lymph nodes; serosa; resection margin)
- Quality of life (EuroQol EQ-5D, EORTC QLQ C-30, EORTC QLQ-CR29)
- Surgical morbidity/mortality
- Predictive value of tumour biomarkers in terms of predicting response to artesunate therapy
- Biomarker and molecular profiling studies

# 17.3 Sample size and recruitment

#### 17.3.1 Sample size calculation

We performed our sample size calculation largely based on inferences drawn from our pilot Phase I study (Krishna *et al.*, 2015). The input assumes that the analysis would be conducted using a univariate Cox proportional hazard survival model from the time of surgery to the first disease recurrence with one binary covariate representing treatment groups (artesunate or placebo). We calculated that a minimum sample size of 168 patients is necessary to test a hazard ratio (HR) of 0.56 for the intervention versus placebo. This value is within the confidence intervals estimated in our phase I study (Krishna *et al.*, 2015) and somewhat between the point estimate in the worse case scenario inference in the paper and a value of 0.7 commonly circulated in oncology clinical trials. For this Phase II study, we set the power at 0.8 and accepted a type one error of 0.1 for a one-sided test.

- 1) The null nypothesis H0: HR=0.56 (equivalent ≤)
- 2) The alternative hypothesis H1: HR>0.56

These settings would result in a sample size of 168 patients. Inflating this sample size by 15-20% to allow for loss at follow-up would result in approximately 194-202 patients. We believe that 200 patients therefor represents a feasible and achievable target given our time and financial constraints.

The rationale and sensitivity analyses for these calculations are outlined below. The general setting is that of a survival analysis where the event is defined as the first disease recurrence after surgery.

A cohort of Stage II/III colorectal cancer patients undergoing surgery will be randomised as per recruitment to receive the artesunate intervention or placebo. Patients will be followed-up for 5 years following surgery. The minimum sample size to test a hazard ratio (HR) of 0.56 for the intervention vs. placebo group is based on:

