# 4. Primary Objective

The primary objective of the study is to determine if neoadjuvant oral artesunate improves progression free survival at 2 years in Stage II/III colorectal cancer compared to standard treatment with surgery alone +/-adjuvant post-operative chemotherapy where indicated.

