The minimum sample size has been calculated within the same general circumstances and similar outcome (disease recurrence) as the pilot study. Namely, the calculations are initially based on the HR of treatment group versus placebo group values ranging from 0.15-0.31 as obtained in our pilot study (assuming a 1:1 randomization). The overall ratio of events (disease recurrence) was 0.32 (7/22). However, given the small sample size of the pilot study, we have extended our sensitivity analysis up to the value of 0.56 for the hazard ratio and the corresponding sample size to 200 patients (see graph 1 and table 2). May we add that, under the assumption that the intervention is not worse, the numbers would also be valid for a setting in which one-sided alpha level of significance is set at 0.15 and HR = 0.6 and for one sided alpha level of significance of 0.05 and HR = 0.5 – with power held at 0.8.

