# 17.3.3 Statistical analysis plan

The event of interest (failure defined as cancer recurrence from a survival analysis perspective) is defined as the first recurrence of the disease after the patients' treatment allocation and surgery. Patients will be followed-up for 2 years; if the event of interest does not occur the patient will be considered (right) censored. The general assumption for time-to-event (survival analysis) is that the censoring is non-informative, i.e. it is independent of the event process. The Cox proportional hazard (PH) model would be applied to investigate the hazard ratio of disease recurrence for the artesunate group versus placebo group. The semi-parametric technique allows no assumption to be made on the baseline hazard; nevertheless proportionality of the hazards in the two arms should hold. The latter assumption can be tested on the basis of Shoenfeld residuals after fitting the model to the data.

We discussed an interim analysis in December 2021 with the DMC and TSC. At this time point 78 patients will have reached the primary end point (recurrence free survival 2 years after surgery). This analysis will be performed by an independent trial statistician familiar with both trials ([name]) and a report presented to the DMC and TSC members for review and recommendations thereafter.

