The inference is expressed in survival type metrics: i.e. proportion of individuals surviving recurrence beyond 1 year, 2 years and median time to recurrence in each group. Predictions (survival prognostics) will refer to the colon cancer population within our data range.

Missing data (attrition) will be assessed and sensitivity analysis will be employed upon the particularities exhibited by the data, i.e. missing data pattern and whether the missing information is associated with the main outcome. This will include data analysis under a 'missing at random assumption' and imputation methods tailored to interval censored data will also be applied.

Both a frequentist and Bayesian framework for statistical inference are envisaged. The uncertainty will be expressed in terms of 95% confidence intervals (CI) or 95% credible intervals (CrI) for their corresponding estimates. The frequentist statistical significance would be deemed at the 0.05 (5%) level.

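### The stated hypotheses are reversed for a superiority trial: the target benefit (HR ≤ 0.56) is the null, and no effect and harm sit in the alternative

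*Protocol*

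**What the plan says.** Section 17.3.1 gives the only formal hypotheses in the protocol. The null is "H0: HR=0.56 (equivalent ≤" and the next line reads "The alternative hypothesis H1: HR>0.56". The same section sets power at 0.8 and a one-sided type I error of 0.1. Its calculation framework defines the HR as the hazard of recurrence in the treatment group against placebo, so values below 1 favour artesunate.

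Section 4 gives the purpose of the trial as to "determine if neoadjuvant oral artesunate improves progression free survival at 2 years" compared with standard treatment. Later in 17.3.1, other combinations of level and HR are offered "under the assumption that the intervention is not worse".

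The analysis text in 17.3.3 says that a Cox model will be used to "investigate the hazard ratio of disease recurrence for the artesunate group versus placebo group". It names no null value. On the level, section 17.2.1 says "Statistical significance will be assumed at the 5% level unless otherwise indicated", and section 17.3.3.1 says, without that qualification, "The frequentist statistical significance would be deemed at the 0.05 (5%) level".

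**The concern.** In a superiority trial the null is no benefit (HR ≥ 1), and the type I error is the risk of claiming benefit for a drug that has none. Here the target benefit is the null. Taken literally, three things follow.

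- The 10% error rate is the risk of wrongly rejecting a drug that meets its target. It does not limit false claims of efficacy.
- The 80% power is power to detect that an inert drug misses the target.
- A significant result shows a shortfall from 0.56, and a non-significant one does not establish HR < 1. Values between 0.56 and 1 are real benefit, yet they lie in the alternative.

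What is at stake is the meaning of the primary test. Sections 17.3.3 and 17.5 also describe an interim analysis dated December 2021, with 78 patients at the primary endpoint. If the success criterion stays unclear, it could be settled after data have been seen.

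**Working it through.** **Inputs, all from 17.3.1:** HR 0.56, one-sided α = 0.10 (z = 1.28), power 0.80 (z = 0.842), allocation P = 0.5, event proportion 0.32 (7/22 in the pilot).

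**The protocol's own figure.** D = (1.28 + 0.842)² / [0.5 × 0.5 × (ln 0.56)²] = 4.503 / 0.0840 = 53.6, so 54 events. N = 53.6 × 100/32 = 167.4, so 168 patients. Both reproduce. The formula depends only on (ln HR)², the squared distance between 0.56 and 1 on the log scale. It therefore fits a test of HR = 1 against 0.56 and a test of 0.56 against 1 equally well, and cannot show which was meant.

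**The test as written, at 54 events.** SE(ln HR) = 2/√54 = 0.2722. Reject if ln(observed HR) > ln 0.56 + 1.2816 × 0.2722 = −0.2310, that is, if the observed HR exceeds 0.794. The probability of rejection is Φ[(ln(true HR) + 0.2310)/0.2722]:

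| True HR | P(reject written H0) |
|---|---|
| 0.56 (target met) | 10% |
| 0.70 | 32% |
| 0.80 | 51% |
| 1.00 (no effect) | 80% |
| 1.20 (harm) | 94% |

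The chance of not rejecting for an inert drug is 1 − 0.802 = 19.8%.

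**A superiority test on the same events.** For H0: HR ≥ 1, the rejection limit is exp(−z × 0.2722), and power at HR 0.56 is Φ(0.5798/0.2722 − z) = Φ(2.130 − z):

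| Level | Reject if observed HR is below | Power at HR 0.56 |
|---|---|---|
| one-sided 0.10 | 0.706 | 80% |
| one-sided 0.05 | 0.639 | 69% |
| two-sided 0.05 | 0.587 | 57% |

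**A result where the readings diverge.** Take an observed HR of 0.75.
- Against the written null: z = (ln 0.75 − ln 0.56)/0.2722 = 1.07, one-sided p = 0.14, so it is not rejected.
- Against HR = 1: z = −1.06, one-sided p = 0.145, 95% CI 0.44 to 1.28.

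The target is not refuted, and benefit is not shown either.

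**Size if a 5% level is chosen.** The same formula at HR 0.56 gives 73.6 events at one-sided 0.05, which is the protocol's own table row of 74 events and 230 patients. At two-sided 0.05 it gives 93.4, so 94 events and 292 patients.

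**The case against.** The strongest reply is that this is a slip of wording in the sample-size rationale. The objective is plainly superiority. The value 0.56 is chosen as a target effect, between the pilot's worst-case estimate and 0.7. The Cox analysis sections never tell anyone to compare the estimate with 0.56. Events, patients, endpoint, model and estimate are the same in either direction. Superiority is indeed the likely intention, and the sample size is untouched. But the analysis sections do not supply the missing null, so the reversed pair is the only statement of what the primary test tests. An analyst who followed it would misread a significant result.

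Four narrower points deserve weight.

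- The 20% chance of success for an inert drug applies only if non-rejection were counted as success. The protocol does not say so, and the figure is hypothetical.
- The phrase about the intervention not being worse may simply justify one-sided testing. It is weak evidence of a comparison with HR = 1, and the conclusion does not need it.
- The conflict over the significance level is a separate defect. Section 17.2.1 allows exceptions and 17.3.1 can be read as one, but 17.3.3.1 states 5% without exception. A decision rule needs both a null and a level, so one amendment should settle both.
- The limit of 0.71 belongs to 54 events. With 200 patients, an event proportion of 0.32 and no loss, there would be 64 events and a limit of exp(−1.2816 × 2/√64) = 0.73. It illustrates the test and should not become a fixed cut-off.

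**Conclusion.** The concern holds. Section 17.3.1 contradicts the objective in section 4, no futility design is declared that would justify the written direction, and the two hypothesis lines agree with each other, so an extraction error is unlikely. Taken literally, the test rejects 80% of the time when artesunate does nothing and 10% of the time when it exactly meets its target. It cannot demonstrate efficacy.

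The fault lies in the hypotheses and in what the error rates protect, not in the 54 events or 168 patients. The probabilities assume 54 events, 1:1 allocation, proportional hazards and the usual normal approximation for the log hazard ratio. Only the protocol was available. A correct statement in a separate analysis plan would not remove the need to correct this one. It must be fixed because it defines the primary test.

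**What to change.** Restate the pair in 17.3.1 as H0: HR ≥ 1 against H1: HR < 1, and name HR = 0.56 as the design alternative at which power is 80% with one-sided α = 0.10. In the same change, state in 17.2.1, 17.3.1 and 17.3.3.1 the one level and sidedness that decide the primary test. Specify the test and its level, not a numerical HR cut-off; about 0.71 at 54 events can be given as an illustration.

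Make the change by dated amendment, described as a textual correction. State whether the interim analysis of the primary endpoint described for December 2021 took place, and who had seen its results when the correction was made.

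The cost is two lines of hypothesis text and one sentence on the level. At one-sided 0.10 the size stands. Choosing 5% with power kept at 80% raises it to 74 events and 230 patients (one-sided) or 94 events and 292 patients (two-sided), both before allowance for loss to follow-up. Keeping 54 events would mean accepting 69% or 57% power.

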#### Calculation framework:

- 1. The minimum sample size calculation has been calculated as for a univariate Cox proportional hazard survival model with one binary covariate representing treatment groups (artesunate or placebo).
- 2. The necessary number of events are calculated as

[figure not shown]
$$D = (Z_{1-\alpha} + Z_{1-\beta})^{2} \left[ P \times (1 - P) \times (\log(HR))^{2} \right]^{-1}$$

Where P represents the proportion of the sample assigned to the treatment group (0.5 corresponding to a 1:1 treatment assignment in our setting) and the HR is the estimated hazard ratio of the event (disease recurrence) for the treatment group vs. placebo. The values of the inverse of the standard normal cumulative distribution function are

 $Z_{1-\alpha}=1.28$  for one sided  $\alpha$ =0.1 and  $Z_{1-\beta}=0.842$  for  $\beta$ =0.20 (equivalent to 80% power).

3. Hence, the minimum total number needed for the trial is calculated as

$$N = D \times (100/32)$$

Graph 1: Study sample size- a sensitivity analysis to various settings for hazard ratios and type one error for one-sided test.

Total number	One sided level of	HR	Number of events
participants	significance		
53	.15	4	17
56	.15	.4 .41	18
59	.15	.41	19
62	.15	.42	20
66	.15	.43	22
70	.15	.45	23
74	.15	.46	24
78	.15	.47	25
82	.15	.48	27
87	.15	.49	28
92	.15	.5	30
104	.15	.52	34
117	.15	.54	38
132	.15	.56	43
149	.15	.58	48
169	.15	.6	55
193	.15	.62	62
222	.15	.64	72
256	.15	.66	82
297	.15	.68	96
347	.15	.7	112
68	.1	.4	22
71	.1	.41	23
75	.1	.42	24
80	.1	.43	26
84	.1	.44	27
89	.1	.45	29
94	.1	.46	31
99	.1	.47	32
105	.1	.48	34
111	.1	.49	36
118	.1	.5	38
132	.1	.52	43
149	.1	.54	48
168	.1	.56	54
190	.1	.58	61
216	.1	.6	70
247	.1	.62	80
283	.1	.64	91
327	.1	.66	105
379	.1	.68	122
443	.1	.7	142
93	.05	.4	30
98	.05	.41	32
103	.05	.42	33
109	.05	.43	35
115	.05	.44	37
122	.05	.45	40
129	.05	.46	42
136 144	.05	.47	44
152	.05	.48 .49	47 49
	.05 .05	.5	52
161			
181	.05	.52	58
204	.05 .05	.54	66 74
230		.56	
261	.05 .05	.58	84
207	U.S.	.6	96
297			100
339	.05	.62	109
			109 125 144

608	.05	.7	195

Table 2: Details sensitivity analyses to various settings for hazard ratio values. Power is set at 0.8.

The minimum sample size has been calculated within the same general circumstances and similar outcome (disease recurrence) as the pilot study. Namely, the calculations are initially based on the HR of treatment group versus placebo group values ranging from 0.15-0.31 as obtained in our pilot study (assuming a 1:1 randomization). The overall ratio of events (disease recurrence) was 0.32 (7/22). However, given the small sample size of the pilot study, we have extended our sensitivity analysis up to the value of 0.56 for the hazard ratio and the corresponding sample size to 200 patients (see graph 1 and table 2). May we add that, under the assumption that the intervention is not worse, the numbers would also be valid for a setting in which one-sided alpha level of significance is set at 0.15 and HR = 0.6 and for one sided alpha level of significance of 0.05 and HR = 0.5 – with power held at 0.8.

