#### 4.1 Primary endpoint

The primary outcome measure for the comparison of the artesunate versus placebo group is recurrence free survival 2 years after surgery.

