The first randomized placebo controlled double blind pilot study of artesunate in colorectal cancer randomized 23 patients with resectable colorectal cancer to receive either 14 daily doses of artesunate or placebo (Krishna et al., 2015). During a median follow up time of 42 months, 1 patient in the artesunate group developed recurrent colorectal cancer compared to 6 patients in the placebo group. Six patients receiving artesunate and 4 patients receiving placebo had measurable Carcinoma Embryonic Antigen (CEA) levels. Three patients in the placebo group had a rise in their CEA on rechecking their levels after the trial intervention whereas no patients in the artesunate group experienced a rise in their CEA levels (p=0.03). In one patient receiving artesunate there was a 75 % reduction in circulating CEA level after 2 weeks of artesunate treatment alone. Patients in the artesunate arm showed a high probability of a reduction in the ki67 proliferation index marker on tumour immunohistochemical analysis compared to those in the placebo arm. Artesunate was generally well tolerated apart from 2 cases of Grade 3 neutropenia and anaemia with one of the cases undergoing a spontaneous recovery of neutrophils and the other requiring granulocyte colony stimulating factor (GCSF). Both patients received a blood transfusion and went on to have surgery with no further complications.

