#### 17.3.3.1 Summary of baseline data and flow of patients

Details of the number of patients eligible for the trial, the number of patients consenting and the number randomised along with a breakdown for each group of the numbers of participants assigned, receiving the intended treatment, completing the study protocol, and analysed for the primary outcome will be clearly documented. This information will be displayed as a flow diagram (http://www.consort-statement.org/).

The analyses will be performed in STATA (StataCorp. 2014. Stata Statistical Software: Release 14. College Station, TX: StataCorp LP.) and/or (R: A language and environment for statistical computing. R Foundation for Statistical Computing, Vienna, Austria. ISBN 3-900051-07-0, URL http://www.R-project.org/). GraphPad (Prism) or other comparable statistical package.

Descriptive statistics, preliminary analysis and graphics will be used to understand the data structure, the nature of the variables and the appropriateness of the subsequent tests and analyses. Data will be summarized as mean, standard deviation and range if normally distributed. If the data are skewed then additional statistics such as median and inter-quartile ranges will be used to correctly describe the selected sample in the population. Parametric or non-parametric tests will be used as appropriate to ensure/verify that the two groups do not differ statistically with respect to any aspects but the intervention.

Three safety interim analyses are planned as the trial data collection proceeds, approximately after 10%, 50% and 75% of patients have completed their day 28 assessments.

The appropriate statistical framework for the analysis of the primary outcome is that of a survival analysis. Patients will be followed-up up to 2 years; if the event of interest does not occur within this time frame, the patient is considered (right) censored. The general assumption is that the censoring is independent of the event process. The Cox proportional hazard (PH) model would be applied to investigate the hazard ratio of disease reccurrence for the artesunate group vs. placebo group. The semi-parametric technique allows no assumption to be made on the baseline hazard; nevertheless proportionality of the hazards in the two arms should hold. The latter assumption can be tested on the basis of Shoenfeld residuals after fitting the model to the data.

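### Section 17.3.1 sizes the trial on a 32% recurrence proportion seen over a median of 42 months, but the primary analysis censors at 2 years, so the 80% power is unsupported

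*Protocol*

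**What the plan says.** Section 17.3.1 specifies a hazard ratio of 0.56, a one-sided type I error of 0.10 and 80% power. The Calculation framework obtains the number of events D from the Schoenfeld formula and then converts events to patients: "Hence, the minimum total number needed for the trial is calculated as" N = D × (100/32). The text after Table 2 gives the source of the 32: "The overall ratio of events (disease recurrence) was 0.32 (7/22"), from the pilot with both arms pooled. The result is 54 events and 168 patients, raised to a target of 200 for 15–20% loss to follow-up.

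The pilot recurrences are described in section 6.8: "During a median follow up time of 42 months, 1 patient in the artesunate group developed recurrent colorectal cancer", against six on placebo. One plus six gives the seven events.

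The primary endpoint (section 4.1) has a shorter horizon: "The primary outcome measure for the comparison of the artesunate versus placebo group is recurrence free survival 2 years after surgery". So does the analysis. Section 17.3.3 says: "Patients will be followed-up for 2 years; if the event of interest does not occur the patient will be considered (right) censored". Section 17.3.3.1 repeats it: "if the event of interest does not occur within this time frame, the patient is considered (right) censored". The sample size rationale itself mentions only the longer schedule: "Patients will be followed-up for 5 years following surgery".

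Table 2 is the only sensitivity analysis. Its caption reads: "Details sensitivity analyses to various settings for hazard ratio values. Power is set at 0.8". It varies the hazard ratio and alpha, not the event proportion.

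**The concern.** Power in a Cox or log-rank comparison is set by the number of events in the analysis. Dividing 54 by 0.32 yields enough patients only if 32% of them recur inside the analysis window. That window is 24 months, while the 32% accrued over a median of 42 months. The protocol neither gives a 24-month figure nor argues that nearly all recurrences happen by then.

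If fewer than 32% recur by 24 months, 168 evaluable patients yield fewer than 54 events and power falls below 80%. The step from 168 to 200 is already allotted to loss to follow-up, so it is not a reserve for the shorter horizon. The two fallback settings offered after Table 2 (alpha 0.15 with hazard ratio 0.6; alpha 0.05 with hazard ratio 0.5) rest on the same 32%.

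**Working it through.** **Inputs.** Hazard ratio 0.56, one-sided alpha 0.10, power 0.80, 1:1 allocation (17.3.1); event proportion 0.32 from 7/22 (text after Table 2); median pilot follow-up 42 months, with 1 and 6 recurrences (6.8); censoring at 24 months (17.3.3, 17.3.3.1).

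**Reproducing the plan's figure.** D = (1.2816 + 0.8416)² / [0.25 × (ln 0.56)²] = 53.6, so 54 events. N = 53.6 / 0.32 = 167.6, so 168. Both agree with the protocol.

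**Does Table 2 vary the event proportion?** D/0.32 against the printed N:

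| One-sided alpha | HR | D/0.32 | Printed N |
|---|---|---|---|
| 0.15 | 0.56 | 131.1 | 132 |
| 0.15 | 0.60 | 169.0 | 169 |
| 0.10 | 0.50 | 117.3 | 118 |
| 0.10 | 0.56 | 167.6 | 168 |
| 0.10 | 0.70 | 442.9 | 443 |
| 0.05 | 0.50 | 160.9 | 161 |
| 0.05 | 0.56 | 229.9 | 230 |
| 0.05 | 0.70 | 607.5 | 608 |

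All eight rows checked use 0.32.

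**Power by 24-month proportion.** With d events, power = Φ(√(d/4) × 0.5798 − 1.2816), where 0.5798 = −ln 0.56.

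| Pooled 24-month recurrence | Events, power from 168 evaluable | Events, power from 200 without loss |
|---|---|---|
| 20% | 34, 66% | 40, 71% |
| 25% | 42, 73% | 50, 78% |
| 27% | 45, 75% | 54, 80% |
| 32% | 54, 80% | 64, 85% |
| 35% | 59, 83% | 70, 87% |

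**Which row applies?** The protocol does not say, so each of these scenarios rests on an assumption.

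- (a) Pooled 32% carried over, constant hazard, everyone followed for 42 months: 1 − 0.68^(24/42) = 19.8% by 24 months. That is 33 events and 65% power from 168, or 40 events and 71% from 200.
- (b) Pooled 32% carried over, with 75–90% of recurrences by 24 months: 168 × 0.32 × 0.75 = 40 events to 168 × 0.32 × 0.90 = 48 events; power 71–77% from 168.
- (c) Rebuilt from the placebo arm: six recurrences in an assumed 10, 11, 12 or 13 placebo patients at 42 months, constant hazard, artesunate survival = placebo survival^0.56. Pooled 24-month recurrence is 33.1%, 29.3%, 26.3% or 23.9%; 168 patients give 56, 49, 44 or 40 events and 81%, 77%, 74% or 71% power.
- (d) As (c), but with 80% of the 42-month recurrences by 24 months instead of a constant hazard. Pooled 42-month recurrence is 50.1%, 45.1%, 41.1% or 37.7%; multiplied by 0.80 × 168 this gives 67, 61, 55 or 51 events and 86%, 84%, 81% or 78% power.

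**Sampling error.** Before any question of timing, the exact 95% confidence interval for 7/22 is 13.9–54.9%. That corresponds to 23–92 events and 55–93% power from 168.

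**What 54 events would require.** Solve [p + 1 − (1 − p)^0.56]/2 = 53.6/N for the placebo proportion p. With N = 168, p = 39% and artesunate is 24%. With N = 200 and no loss, p = 33% and artesunate is 20%.

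**The case against.** The strongest reply is that no shortfall has been shown. Several scenarios in (c) and (d) reach 80%, and the interval for 7/22 includes values well above it. This stands: the defect is an input that does not fit the analysis, not a proven loss of power.

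Scenarios (a) and (b) can fairly be called pessimistic. They carry over a pooled rate pulled down by a pilot artesunate arm whose hazard ratio was 0.15–0.31, then compute power at 0.56. Scenarios (c) and (d) avoid this and are milder, so (a) should not be read as the expected result.

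Patients lost before 24 months also contribute events until they leave, so 168 evaluable and 200 without loss are the two extremes. Under (c), with 200 randomised and 16% exponential loss over 24 months, power is about 84%, 80%, 77% or 74% for placebo arms of 10, 11, 12 or 13. This narrows the gap but still falls on both sides of 80%.

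Counting deaths or persistent disease as events would raise the total. Section 17.3.1, however, defines the event as first recurrence, and the pilot ratio counts recurrences only.

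Finally, Table 2 has an events column, so a reader who knew the expected events could read off the detectable hazard ratio. The missing piece is the proportion needed to get there.

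**Conclusion.** The concern holds. The 54 events and 168 patients are correctly computed, but the 32% that links them was observed over a median of 42 months and is applied to an analysis that stops at 24. Nothing in the protocol bridges the two, so the 80% power at a hazard ratio of 0.56 is not supported for the planned primary analysis.

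The size of any shortfall cannot be settled from the protocol, because recurrence times and pilot arm sizes are not given. In the scenarios above, power from 168 evaluable patients runs from about 65% to 86%. Reaching 80% needs pooled 24-month recurrence of about 32% with 168 patients, or about 27% with 200 and no loss. The mismatch itself is certain; its consequence depends on assumptions. It should be fixed, since the recruitment target and the power statement rest on this one input.

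**What to change.** In section 17.3.1, replace the 32% with a stated and justified 24-month event proportion, given by arm at a hazard ratio of 0.56. Restate expected events and power, or the hazard ratio detectable with 80% power, for 168 and 200 patients. Add a sensitivity range for the event proportion beside those for the hazard ratio and alpha. The benchmark to defend is about 39% on placebo and 24% on artesunate with 168 patients, or 33% and 20% with 200 followed without loss.

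One possible source is the blinded pooled 24-month recurrence among the 78 patients whom section 17.3.3 expected to have reached the primary endpoint by December 2021, if those data exist; no split by arm is needed. Its limits should be stated. Malaysia opened only in Q4 2024 and supplies 120 of the 200 patients, so the 78 are not Malaysian, and section 17.3.2 itself calls the populations different. Precision is also modest: an assumed 20/78 would be 26%, with an exact 95% confidence interval of 16–37%.

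A minor addition would be a phrase in 17.3.1 saying that the 5-year follow-up is not the horizon of the primary analysis.

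The cost is one input, one short table and a few sentences, with no change to the endpoint or analysis time. The stated power may become less favourable. At 19.8% recurrence it is about 65–71%, and the hazard ratio detectable with 80% power, exp(−2.123/√(d/4)), is about 0.48 with 168 patients or 0.51 with 200. No extra patients are needed if the restated power is accepted. Keeping 80% at 0.56 would take 53.6/p evaluable patients: about 272 at 19.8%, 215 at 25% or 199 at 27%.
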